4. MATERIALS AND METHODS

The present study will be characterized as a randomized, double-blind, placebo-controlled clinical trial. The sample calculation was based on the current prevalence of ASD in children according to the latest release from the Center for Disease Control, with a target of 270 volunteer participants with ASD, maintaining a confidence interval of 5%.

Pre-screening will have immediate action, and volunteers can register by filling out a virtual recruitment questionnaire available on the website www.gon1.com.br. This phase is crucial in raising sponsorship funds to ensure the feasibility of the research, considering the minimum sample safety requirements. It is emphasized that the analysis of inclusion criteria and contact with families will only be conducted after the project approval by this Research Ethics Committee.

The safety of using the probiotic mix will be ensured by the results obtained from toxicity and pathogenicity tests and by defining the supplement ceiling (zinc 20% 0.148g, selenium 1% 0.032g + magnesium 65mg + vitamin A 0.300g) contained in the K11-Tmax version according to the positive list from ANVISA stratified at the age of 3 years.

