4.1. SAMPLE SELECTION

Inclusion Criteria:

- Volunteers must have a confirmed diagnosis of ASD conducted by qualified professionals, according to the criteria established in the Diagnostic and Statistical Manual of Mental Disorders (DSM-5) or another recognized diagnostic classification.
- The study will include children and adolescents in the specific age range of 3 to 11 years.
- Must be regularly enrolled in a public or private school, or in a special education center.
- Absence of uncompensated clinical or psychiatric comorbidities.
- Informed consent: Legal guardians must provide informed consent, understanding the study objectives, procedures involved, risks and benefits, as well as the freedom to withdraw from the study at any time.
- Informed assent: Children aged 7 to 11 years must provide informed assent, understanding the study objectives, procedures involved, risks and benefits, as well as the freedom to withdraw from the study at any time.

Exclusion Criteria:

- Concomitant restrictive medical conditions that may interfere with study results, such as severe gastrointestinal diseases, significant metabolic diseases, or immunodeficiencies.
- Use of specific medications such as broad-spectrum antibiotics or immunosuppressive drugs during the follow-up period.
- Allergies or intolerances to components of the probiotics that will be administered.
- Previous or current participation in recent clinical studies with distinct therapeutic interventions.
- Uncontrolled cardiac conditions or severe unstable medical illnesses.
- Inability to be present on the predetermined dates of clinical assessments.

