4.2. EXPERIMENTAL PROTOCOL

4.2.1. Study Design

This study will be conducted in a medical clinical specifically adapted for testing and with a permissive playful space to mitigate the stress of the involved children and avoid social conflicts during evaluation sessions. The space will comprise at least 17 individual analysis rooms, and the evaluation will involve 20 neuropsychologists, 2 pediatricians and 1 psychiatrist with prior and ensured training.

Children will be evaluated on DAY 0, DAY 45 and DAY 90 to quantify inflammatory markers through blood collection; for measuring fecal calprotectin, by collecting fecal samples; and finally, for the primary outcomes mentioned in this project: neuropsychological (Vineland-3); psychiatric (ADOS) and psychopedagogical (CARS). After the first data collection, individuals will be randomized to receive the K11-T probiotic mixture or the K11-Tmax probiotic mixture or placebo, in a 1:1:1 ratio. After the initial 90-day follow-up, up to 30% of the sample using K11-Tmax will continue to be monitored, being re-evaluated after 365 days in all aspects mentioned. Children will be stratified by age, gender and level of support (see Appendix B) and then randomized to intervention according to the groups below.

Condition or Disease	Intervention/Treatment	Phase
Children with ASD	Drug 1: Probiotic K11-T Drug 2: Probiotic K11-Tmax Drug 3: Placebo	Phase 3

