4.2.11. Biostatistics

Mean and SD (standard deviation) will be used to describe quantitative data, while risk factors, frequency and percentage will be used to describe qualitative data. Shapiro-Wilk test will confirm or not the normality of data distribution in the groups, therefore, parametric, or non-parametric tests, respectively, will be used to assess the research variables. To compare quantitative variables in the two or more groups, independent t-test (between groups) or paired samples t-test (within groups), ANOVA (between groups) or Repeated Measures (within groups), with post hoc testing to assess individual differences among the categories, will be used as parametric options. The relatives nonparametric options will be used otherwise and chi square test, if qualitative variables. All statistical calculations will be performed at the significance level of less than 0.05 (P < 0.05). Data will be analyzed using SPSS version 26.0.

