6. PROPOSED SCHEDULE

The literature review and volunteer registration (pre-recruitment) commenced prior to the review of this project by the Research Ethics Committee (REC), owing to the imperative to review existing literature for document preparation and ensure the minimum sample size feasibility for the investor, thereby facilitating project execution.

Scheduled Activity	Month (2024)											
	Jan	Feb	March	April	May	Jun	Jul	Aug	Sept	Oct	Nov	
Literature review	X	X	X	X	X	X	X	X				
Pre-recruitment of volunteers and posting of the project on the CEP		X	X									
Conducting neuropsychological evaluations (Vineland-3)				X	X		X					
Conducting psychiatric evaluations (ADOS)				X	X		X					
Conducting psychopedagogical evaluations (CARS)				X	X		X					
Blood collection and analysis of fecal material				X	X		X					
Questionnaire completion				X	X		X					
Data tabulation of demographic and anthropometric data							X	X				
Statistical analysis of the data								X	X			
Presentation of the data at scientific events										X	X	
Preparation of the scientific article for publication in indexed journal										X	X	

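### The fixed t-test/ANOVA and repeated-measures analyses discard the earlier scores of children who leave before Day 90; a mixed model in the same software would use them and protect the arm comparison

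*Protocol*

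**What the plan says.** Protocol 4.2.1 states that "Children will be evaluated on DAY 0, DAY 45 and DAY 90", names Vineland-3, ADOS and CARS as the primary outcomes, and says that "individuals will be randomized to receive the K11-T probiotic mixture or the K11-Tmax probiotic mixture or placebo, in a 1:1:1 ratio". Section 4 sets the target at 270 children, so 90 per arm.

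Section 4.2.11 names the analyses. Between groups it gives the independent t-test or ANOVA, and within groups the paired t-test or repeated measures: "ANOVA (between groups) or Repeated Measures (within groups), with post hoc testing to assess individual differences among the categories". Nonparametric counterparts are used if normality fails, and the software is SPSS 26. The section does not say whether the between-arm test compares Day 90 scores or changes from Day 0.

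Three items in section 4.1 bear on who reaches Day 90:
- Guardians, and children aged 7 to 11, are told of the study's procedures, risks and benefits, "as well as the freedom to withdraw from the study at any time".
- One exclusion criterion is "Inability to be present on the predetermined dates of clinical assessments".
- Another is the use of broad-spectrum antibiotics or immunosuppressants while follow-up is under way, which can be known only after randomisation.

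Section 4.1 does not say whether the two exclusions stop applying once a child is randomised. It also does not distinguish stopping the product from leaving the study.

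**The concern.** Each named test needs particular measurements on each child. A paired or repeated-measures test needs every visit it covers, and an ANOVA of Day 90 or of change needs Day 90. The rank-based counterparts have the same need. A child seen at Day 0 and Day 45 who then leaves adds nothing to a Day 90 comparison, although two of the three scores are in hand.

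Families can see by Day 45 whether the child has changed. If that affects who stays, and does so differently by arm, the children left at Day 90 no longer represent the arms as randomised. The contrast between product and placebo is then partly a contrast between those who stayed. The wording of 4.1 adds to the risk: a randomised child who later takes a listed drug or cannot attend a date could be read as excluded, which would create the missing scores by rule.

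**Working it through.** **What each test keeps (from 4.2.1 and 4.2.11).**

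| Child's record | Between-arm ANOVA, Day 90 or change | Within-group repeated measures, three visits |
|---|---|---|
| Days 0, 45, 90 | used | used |
| Days 0 and 90 (misses Day 45) | used | not used |
| Days 0 and 45 (leaves) | not used | not used |

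A child who stops the product but attends all visits is used by both.

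**When loss biases the arm comparison.** Let d be the share lost in an arm and g the mean of children kept minus the mean of children lost. The kept mean exceeds the full-arm mean by d × g, so the bias in the difference is dA·gA − dP·gP.
- 20% lost in both arms, g = 0.5 SD in both: 0.10 − 0.10 = 0.
- 20% v 10%, g = 0.5 SD in both: 0.10 − 0.05 = 0.05 SD.
- 20% on active with g = 0.5 SD, loss on placebo unrelated to outcome: 0.10 SD.

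**Scenario A: loss driven by early change.** The protocol gives no dropout rate or between-visit correlation, so these are assumptions: 90 per arm (270/3); SD 15, the Vineland-3 metric in 4.2.8; correlation 0.8 between any two visits; active loss 10% at random; placebo loss about 20%, logistic in the standardised Day 0–45 change with slope 0.7 or 1.5, so that children with little change leave. The true Day 90 effect is 0 or 4 points, half of it present at Day 45. There were 5,000 simulated trials per case.

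| | slope 0.7 | slope 1.5 |
|---|---|---|
| Completers' change, true effect 4 | 3.37 | 2.93 |
| Likelihood-type estimate using leavers' Day 0 and Day 45 scores, true effect 4 | 4.00 | 4.02 |
| Raw Day 90 difference, true effect 4 (repeat run) | 4.01 | 4.08 |
| Completers' change, bias with no effect | −0.63 | −1.08 |
| Two-sided rejection with no effect, change score | 6.8% | 11.4% |

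The bias matches d × g: 0.63/0.20 = 3.2 points and 1.08/0.20 = 5.4 points between stayers and leavers on placebo.

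*Why raw Day 90 escapes.* With variance 225 and equal covariances of 0.8 × 225 = 180, the covariance of Day 90 with the Day 0–45 change is 180 − 180 = 0. For the Day 0–90 change it is 180 − 180 − 180 + 225 = 45. So the selection touches the change score and not the raw score. This is a feature of the assumed correlations and of what drives the loss.

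*Direction.* SD of change = 15 × √(2 × 0.2) = 9.49. With 81 and 72 completers, SE = 9.49 × √(1/81 + 1/72) = 1.54. By normal approximation:
- Bias −0.63: shift 0.41 SE. Rejections favouring active about 0.9%, favouring placebo about 6.1%.
- Bias −1.08: shift 0.70 SE. About 0.4% and 10.4%.

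The excess rejections therefore go against the product.

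**Scenario B: loss driven by the Day 45 score.** Three arms of 90, correlation 0.7, no true effect, 3,000 trials per case. Higher Day 45 scores raise the chance of leaving in the active arms only; placebo loses 10% at random.

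| Active loss | Bias of raw Day 90 | ANOVA rejection | Bias after regression on Day 0 and Day 45 |
|---|---|---|---|
| 22% | −0.10 SD | 8.3% | about 0 |
| 32% | −0.14 SD | 12.5% | about 0 |
| 34% | −0.23 SD | 26.8% | about 0 |

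Loss unrelated to outcome (10% v 10%, or 20% v 10%) gave bias of about 0 and rejection of 5.2% to 5.5%.

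Here the raw Day 90 ANOVA is the biased analysis. On ADOS and CARS higher scores are worse (4.2.9, 4.2.10), so a negative bias flatters the active arms; on Vineland-3, where higher is better (4.2.8), it counts against them.

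**The case against.** The strongest reply is that 4.2.11 states no complete-case rule. Analysis sets and missing-data handling are commonly set out in a statistical analysis plan, which may exist and is not shown. That stands: their absence is not a fault here. What remains is that the protocol itself names the tests, and for three repeated primary scales those tests use partial records poorly.

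A reader might infer more than the text supports:
- *That a missed visit costs about a fifth of the arm comparison.* If 10% miss each later visit independently, 1 − 0.9² = 19% (about 51 of 270) lack at least one. But repeated measures is labelled as within groups. The Day 90 ANOVA loses 10%, keeping 81 per arm against about 73 for repeated measures.
- *That withdrawal is the only way out.* Section 4.1 also lists follow-up medication and inability to attend as exclusions.
- *That the calendar in section 6 forces missed visits, because June is unmarked.* Day 0 on 2–16 April puts Day 45 on 17–31 May and Day 90 on 1–15 July, which is the marked pattern. The protocol does not say that enrolment runs through all of April.
- *That all three scales are equally exposed.* ADOS needs the child present. CARS is completed by teachers, and Vineland-3 by parents or caregivers and teachers, so a missed clinic day need not lose them. A child who leaves the study could lose all three.

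It is also fair to say that both scenarios make loss depend only on recorded scores. That is the condition under which the likelihood approach is unbiased, so its good result is built in. If loss depends on the unseen Day 90 score, a mixed model does not fully remove the bias.

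**Conclusion.** The point holds in a limited form. The fixed tests leave the earlier scores of leavers unused, and the arm comparison can be biased if loss is related to those scores and differs by arm. It is unbiased if loss is unrelated to outcome, or if both arms lose the same share with the same gap.

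The size is illustrative. In scenario A the change score is off by 0.6 to 1.1 points on an SD of 15, against the active arm, and raw Day 90 scores are about unbiased. In scenario B raw Day 90 scores are off by 0.10 to 0.23 SD. Every dropout rate, slope and correlation is assumed, and only scenario A is set on a trial scale (the Vineland-3 metric). The documents do not support a claim that the plan favours the product, or that bias is certain. The change is worth making because it costs little and the score to be compared is not fixed.

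**What to change.** 1. **Section 4.2.11.** Make the primary between-arm comparison for Vineland-3, ADOS and CARS a linear mixed model (SPSS MIXED) of the Day 45 and Day 90 scores. Include arm, visit, arm-by-visit and the Day 0 score, allow correlation between visits within a child, and report the Day 90 contrasts. Include every randomised child in the assigned arm with whatever visits exist. A child with Day 0 only has no later score to contribute, which makes the next item matter.
2. **Section 4.1.** State that, for follow-up and analysis, the attendance and follow-up-medication criteria are applied at entry. Randomised children who later meet them, or who stop the product, keep their Day 45 and Day 90 assessments and stay in the comparison unless consent to follow-up is withdrawn. This governs assessment and analysis only and changes nothing in clinical management.

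The cost is protocol wording, a procedure in the named software, and the effort of assessing the few children who stopped the product. If loss proves small, the mixed model and the simpler tests should differ little.

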5. JUSTIFICATION

Autism Spectrum Disorder (ASD) is a complex neurobiological disorder characterized by deficits in social communication, restricted and repetitive patterns of behavior, narrow interests, and atypical sensory sensitivities. Although the exact cause of ASD remains unknown, growing evidence suggests the contribution of genetic, environmental, and immunological factors in its development.^{1,2,3,4,6,7,12,14,17,19}

An emerging area of research related to ASD focuses on the role of the intestinal microbiome and its interaction with the immune system and the brain. Studies by Finegold et al. (2002)¹⁰, Kang et al. (2017)⁴⁰, Navarro et al. (2019)⁴, and Adams et al. (2011)³⁹ have demonstrated alterations in the composition and diversity of the intestinal microbiota in children with ASD, as well as a higher prevalence of gastrointestinal disorders compared to neurotypical individuals. These alterations in the intestinal microbiome may be associated with chronic inflammation and immune dysfunction.

In this context, probiotics emerge as a potentially promising intervention for managing ASD symptoms. Probiotics are beneficial live microorganisms that, when administered in adequate quantities, can confer health benefits to the host. They have the potential to modulate the composition and function of the intestinal microbiota, reduce inflammation, and improve gastrointestinal health.^{41,42,43}

Preclinical investigations, exemplified by Hsiao et al. (2013)⁴¹ and initial clinical studies, such as Tomova et al. (2015)⁴², have demonstrated that probiotic supplementation could potentially ameliorate symptoms associated with ASD, encompassing repetitive behaviors, social aptitude, communication, and alleviation of gastrointestinal issues. Nevertheless, it is imperative to emphasize the necessity for additional research endeavors aimed at thoroughly and rigorously assessing the effectiveness of probiotics as a therapeutic modality for children diagnosed with ASD.

Therefore, a study investigating the action of probiotics in improving symptoms manifested due to the disorder in children with ASD is justified. This study would contribute to understanding the underlying mechanisms of probiotic effects on ASD and provide robust scientific data to support probiotic-based therapeutic interventions, potentially positively impacting the quality of life of these children and their families.

6. PROPOSED SCHEDULE

The literature review and volunteer registration (pre-recruitment) commenced prior to the review of this project by the Research Ethics Committee (REC), owing to the imperative to review existing literature for document preparation and ensure the minimum sample size feasibility for the investor, thereby facilitating project execution.

Scheduled Activity	Month (2024)											
	Jan	Feb	March	April	May	Jun	Jul	Aug	Sept	Oct	Nov	
Literature review	X	X	X	X	X	X	X	X				
Pre-recruitment of volunteers and posting of the project on the CEP		X	X									
Conducting neuropsychological evaluations (Vineland-3)				X	X		X					
Conducting psychiatric evaluations (ADOS)				X	X		X					
Conducting psychopedagogical evaluations (CARS)				X	X		X					
Blood collection and analysis of fecal material				X	X		X					
Questionnaire completion				X	X		X					
Data tabulation of demographic and anthropometric data							X	X				
Statistical analysis of the data								X	X			
Presentation of the data at scientific events										X	X	
Preparation of the scientific article for publication in indexed journal										X	X	

7. ESTIMATED COSTS

It is emphasized that the research will be sponsored by Gon-1 Project Management Ltd. - 12.410.656/0001-61, with financial support from an associated sponsor to be defined after the first round of investments from institutions that have already shown interest during the pre-recruitment phase of volunteers, which is carried out after approval by the Research Ethics Committee (CEP).

Expense Type	Expense Amount (R\$)	Public Funding (R\$)	Private Funding (R\$)
Inflammatory Tests	56.487,13		56.487,13
Biochemical Tests	65.196,29		65.196,29
Clinical Assessments (DAY 0 / DAY 45 / DAY 90) and Acquisition of Vineland-3 Test	57.846,00		57.846,00
Clinical Assessments (T180/T365) and Acquisition of Vineland-3 Test	53.923,00		53.923,00
Researchers and Team	280.000,00		280.000,00

Probiotic K11-Tmax	260.000,00		260.000,00
Probiotic K11-T	151.890,00		151.890,00
Placebo	3.559,10		3.559,10
Technical Support for Volunteers	65.800,00		65.800,00
Research Management	360.000,00		360.000,00
Fees and Taxes	144.367,77		144.367,77
General Expenses	38.079,77		38.079,77
Publication	50.000,00		50.000,00
TOTAL			R\$ 1.587.148,88

Annex A

Interview Instrument

Name: _____
Guardian's Name: _____
Gender: _____ Date of Birth: _____
Support Level: () 1 () 2 () 3 Randomization Code: _____
Clinical Comorbidities: _____

Annex B

Autism Diagnostic Observation Schedule (ADOS)

MODULE 1 - 31 MONTHS - PRE-VERBAL AND SINGLE WORDS

1. Free play
2. Name response
3. Response to joint attention
4. Bubble play
5. Anticipation of a routine with objects
6. Response to social smile
7. Anticipation of a social routine
8. Functional and symbolic imitation
9. Birthday party
10. Snack time

Note: Joint attention onset requires spontaneous shifting of gaze between three points - object and person - for the sole purpose of sharing interest or pleasure (may or may not involve pointing gesture).

A three-point gaze shift requires the child to look at the object, then at the person (to catch their gaze and direct it to the object), and then back to the object, or the child looks at the person first, then at the object, and then back to the person.

PARENT GUIDANCE

- Observe how these parents interact with the child.
- Observe the child's reaction to parental stimuli.
- Communicate to parents that from activity 2 onwards (toy block), parental stimulation is not advised unless requested.
- Parental stimulation does alter the score.
- Be cautious with reinforcements, we need to observe whether the child genuinely possesses the skill, as well as the level of autonomy and what she can actually do independently.

1- FREE PLAY

Aspects to observe:

- Does the child attempt to engage the caregiver spontaneously? Requests help looks at parents or therapist.
- If yes, how does she do it?
- Does this involve any type of joint referencing of objects, such as giving and showing to them, or just seeking affection or help?
- How does she communicate if she does?
- Does the child direct her emotions towards others?
- How does she express them?
- Does she explore materials symbolically and functionally?
- Does she remain engaged in activities, quickly shifting from one object to another, or getting stuck in repetitive actions.

2- NAME RESPONSE

Aspects to observe:

- Observe and evaluate the consistency of the child's response to the hierarchy of stimuli.

- What sounds and actions do you or the family member or caregiver need to make to get the child's attention?
- How does the child respond?
- Does she establish eye contact?
- Does she look at your face or in your direction, or look at the family member or caregiver, or in your direction?
- Does she vocalize?

Stimulus Sequence:

1. Call the child by name.
2. Ask the family member or caregiver to call the child by name up to two times.
3. Ask the family member or caregiver to say other words or make a familiar noise or sound.
4. Ask the family member or caregiver to do whatever is necessary, including touching the child, to get her to look at the relative (gestural help).

3- RESPONSE TO JOINT ATTENTION

- Does the child follow a simple gaze shift or follow a gaze shift accompanied by a pointing gesture?
- Pay attention to the child's behaviors when playing with the remote-control toy, including eye contact, vocalizations, requests, shared pleasure, initiations of joint attention, and pretend play (e.g., hugging or kissing the teddy bear).

4- BUBBLE PLAY

Aspects to observe:

- Observe emotions, shared attention, if she points.
- Does the child display stereotypes, atypical motor movements, how is her behavior (participates, ignores, aggressive, irritating...)
- If she has hypersensitivity.

5- ANTICIPATION OF OBJECT ROUTINES

Aspects to observe:

- Observe emotions and the onset of joint attention by the child, shared pleasure, how the child makes requests, motor responses during the activity, especially those repetitive mannerisms, stereotypes.

6- RESPONSE TO SOCIAL SMILE

Aspects to observe:

- Evaluate the child's smile appearance in response to:
 - (a) the smile of the family member or caregiver,
 - (b) the smile of the family member or caregiver combined with the performance of a familiar sound or with you calling in a way that suggests physical contact, but without touching the child (e.g., "I'm going to get you"), Or being touched.

7- ANTICIPATION OF A SOCIAL ROUTINE

Aspects to observe:

- Evaluate the child's emotional reaction and attempt to initiate a routine repetition.
- Pay special attention to the social intent of the child's behaviors and the extent to which she integrates gaze, facial expression, vocalization, and gestures into actions directed toward the examiner or the family member or caregiver, especially those behaviors that are indicative of shared pleasure.

8 - JOINT ATTENTION RESPONSE

- Does the child follow a simple gaze shift or follow a gaze shift accompanied by a pointing gesture?
- Pay attention to the child's behaviors when she's playing with the remote-control toy, including eye contact, vocalizations, requests, shared pleasure, initiations of joint attention, and pretend play (e.g., hugging or kissing the teddy bear).

Guidance:

- Orient the child's body towards your face. Yes, it's possible. Up to FIVE attempts should be made to draw the child's attention to his (the examiner's) face.
- Proceed with the activity. If you fail to get the child's attention, move on to the stimulus hierarchy, including activating the toy.
- Say: "(child's name), look!" (with exaggerated eye gesture).
- Say or name the child and say "look at" (do this) 2 times *
- Use the toy.

9- FUNCTIONAL AND SYMBOLIC IMITATION

Aspects to observe:

- How does the child use miniature objects and substitute to imitate known actions?
- Are these acts performed with social awareness and shared pleasure?

10- BIRTHDAY PARTY

Aspects to observe:

- Evaluate the child's interest and ability to integrate into the "script" of the doll's birthday party.
- Does the child treat the doll as a representation of a living being?
- Does the child contribute spontaneously to the party representation?
- If not, does the child spontaneously imitate the examiner's actions or participate when asked to do so or when directed?
- Pay attention to shared pleasure, initiations, and reciprocity.

11- SNACK TIME

Aspects to observe:

- Does the child indicate a preference for a snack and ask for it?
- If yes, how does she do it?
- How does she use visual cues, gestures, facial expressions, and vocalizations to communicate a request to you and engage in social initiations?
- Does the child show her snack to her family member or caregiver or try to feed adults in the room or share food with them?

MODULE 2 - VERBAL EXPRESSION WITH PHRASES

1. Building task
2. Pretend play
3. Joint interaction game
4. Demonstration task
5. Describing an image
6. Telling a story from a book
7. Cartoons
8. Narration and conversation
9. Emotions

10. Social difficulties
11. Break
12. Friends and marriage
13. Loneliness
14. Creating a story

1- BUILDING TASK

Observation Focus: The observation focus is on determining if the child indicates the need for more pieces and how she does it (e.g., reaching over the examiner's arm, vocalizing, or making eye contact).

Communication sample recording:

2- PRETEND PLAY

Observation Focus: The observation focus is on determining to what extent the child produces sequences of actions involving the use of materials beyond their most obvious intention. Special attention should be given to how the child assigns an animated role to dolls and how she pretends that dolls interact with each other.

3- JOINT INTERACTION GAME

Observation Focus: The observation focus is on the reciprocity demonstrated by the child in interactive play. The goal is for the child (not the examiner) to develop interaction and demonstrate a new initiative that goes beyond a direct response to the examiner's proposals.

4- DEMONSTRATION TASK

Observation Focus: The objective of this task is to determine if and how the child represents familiar actions through gestures, especially using her body to represent an object (e.g., using a finger to represent a toothbrush) or mimicking the use of an imaginary object. Additionally, this task provides an opportunity to assess the narration of a familiar event.

5- DESCRIPTION OF AN IMAGE

Observation Focus: The objective of this task is to obtain an example of the child's spontaneous discourse and communication, as well as to understand what captures her interest.

6- TELLING A STORY FROM A BOOK

The objective of this task, like the previous one, is to obtain an example of the child's spontaneous discourse and communication and to understand what captures her interest. This task also provides an opportunity to assess the extent to which the child can provide a sense of continuity to a story.

7- CARTOONS

Observation Focus: The objectives of this task include (a) observing the use of gestures and their coordination with speech by the subject, (b) observing their response to humor, (c) recording a sample of language, (d) gaining an idea of their degree of insight and flexibility in adapting a narrative to the listener audience, and (e) noting any comments the subject may make about affect and relationships.

8- CONVERSATION NARRATION

Observation Focus: The observation focus is on the subject's ability to move from the examiner's sentences and fully engage in dialogue, particularly about a topic outside the immediate context. Special attention should be paid to how the subject recounts routine and non-routine events and describes relationships and emotions.

9- EMOTIONS

Observation Focus: It has a dual objective: (a) to identify which events or objects elicit different emotions in the participant, especially if they are social or not, and (b) to observe how the subject describes their emotions. Questions:

- What do you do to feel happy or content?
- What kind of things make you feel this way? How do you feel when you are happy? Can you describe (tell me about) it?
- What scares you?
- What makes you feel scared or anxious? How do you feel? What do you do?
- And when you're angry?
- What makes you feel this way? How do you feel "inside" when you're angry?
- Everyone feels sad sometimes. What makes you feel this way?
- How do you feel when you're sad? What happens when you're sad? Can you describe it?

10- SOCIAL DIFFICULTIES

Observation Focus: The observation focus is on the subject's perception of their social difficulties, their insight into the nature of these problems, and whether the subject has made any attempt to change their behavior to better adapt to others. Attention should be paid to the subject's understanding of the appropriateness and implications of their feelings. Questions:

- Have you ever had problems with people at school (or work)?
- Is there anything others do that irritates or annoys you? What?
- Have you ever been teased or threatened? Why do you think that happened?
- And do you do anything that annoys others?
- Have you ever tried to change those things? Have you ever done anything so others wouldn't bother you? Did it work?

• Break:

Observation Focus: (a) how the subject occupies themselves during free time, (b) how they react to the examiner's withdrawal of interaction, and (c) if and how the subject initiates and participates in an unstructured conversation or interaction with the examiner.

• Friends and Marriage:

Observation Focus: It focuses on how the subject perceives the concept of friendship and/or marriage and the nature of these relationships, as well as how they perceive their role in these relationships. Questions about marriage and long-term relationships also focus on the subject's understanding of why a person would want to be in a long-term relationship and their perception of their possible role in such a relationship. Questions:

- Do you have any friends? Can you tell me about them? (Note down their ages, names, occupation.)
- What do you like to do together? How did you meet? Do you spend a lot of time together?
- What does being a friend mean to you?
- What is the difference between a friend and someone you work with or go to school with?
- Do you have a boyfriend/girlfriend? What is their name? How old are they?
- When was the last time you were together?
- What are they like? What do you like to do together?
- How do you know they are your boyfriend/girlfriend?
- Have you ever thought about having a long-term relationship or getting married (when you're older)?
- Why do you think people get married when they get older?
- What do you think about marriage? What are the good parts? What do you think might be difficult?

- Loneliness

Observation Focus: These questions refer to the subject's perception of the concept of loneliness and how they feel about it. Questions:

- Have you ever felt lonely?
- Do you think other kids in your situation also feel lonely?
- Is there anything you do to feel better?

14- CREATING A STORY

Observation Focus: Creative use of objects by the subject to tell a new story or invent the transmission of a news bulletin or advertisement.

MODULE 3 - VERBAL FLUENCY

1. Building Task *
2. Tell a story from a book
3. Description of an image *
4. Conversation and reports
5. Current employment or school *
6. Social difficulties and inconveniences
7. Emotions
8. Demonstration task
9. Video
10. Break
11. Daily life *
12. Friends and marriage
13. Loneliness
14. Plans and aspirations
15. Invent a story

(* OPTIONAL ACTIVITIES)

1- BUILDING TASK (OPTIONAL)

Aspects to observe: The objective of this activity is to observe if the individual indicates the need for more pieces and, if so, how they do it (e.g., reaching over the examiner's arm to grab the pieces, do they vocalize or gesture, or make eye contact?)

Communication sample recording

2- TELL A STORY FROM A BOOK

Aspects to observe: The objective of this activity is to obtain a sample of the participant's language and spontaneous communication and get an idea of what interests them. This task also provides an opportunity to assess their response to conventional humor and their understanding of visual cues in the social context (e.g., what the characters are doing in the story and how they are feeling).

3- DESCRIPTION OF AN IMAGE (SEE PREVIOUS MODULES) - OPTIONAL ACTIVITY

4- DIALOGUE

Aspects to observe: The objective is to observe the extent to which the participant can build a conversation around the examiner's claims and take an active role in the conversation, especially about an issue without immediate context. Special attention should be paid to how the participant reports routine and non-routine events and how they describe relationships and emotions. This task also offers an opportunity to observe the characteristics of their communication including the use of gaze, facial expression, intonation, and gestures.

5- WORK OR SCHOOL

If the individual is in full-time school, has no job, and has never worked (including volunteering outside of school), skip the questions about work and move on to the questions about school. Questions about school:

- Aspects to observe: The objective of the initial questions is to obtain general information about the individual's employment to be able to ask follow-up questions. It is especially interesting to know if the individual has had to leave previous jobs and what the reasons were. These questions also allow assessing if the participant has a realistic view of their future employment possibilities. In addition to expectations about work.

Questions about work:

- Do you have a job?
- If yes, how is it: What kind of work is it? How did you find it? Have you had other jobs before?
- If you haven't: What do you do during the day? Have you had a job before? Why did you leave your previous job, was it planned? Are you happy where you are now or would you eventually like to change to do something else? What else would you do? What should you do to find this type of work?

Questions about school:

- Did you attend school? Where?
- What courses are you taking?
- What grade are you in? How are you doing?
- If the participant is no longer in school and not working, ask: Until which grade did you reach in school? How was it? What do you plan to do next? What experience or training would you need to be able to do that?

6- SOCIAL DIFFICULTIES

Aspects to observe: The focus here is on the participant's perception of their social difficulties, their understanding regarding the nature of these problems, and if they have made any attempt to change their own behavior to better fit in with the people around them. You should pay attention to the degree of understanding the participant has about the implications of their feelings and whether they are appropriate or not. Interview questions:

- Have you ever had difficulty relating to people in school or at work?
- Are there things that others do that annoy or bother you? What are they?
- Have they ever teased or bullied you in any way?
- Why do you think they did that?
- And the things you do that bother others?
- Have you ever tried to change these things? Ever done anything so that others don't make fun of you? Did it work?

7- EMOTIONS

